# Study Protocol

Behavioral Mechanism of Energy Compensation with Exercise  
NCT04651218

October 13, 2022

Visit 1 (week 1). The Study Coordinator will meet with each participant for a 30-minute orientation session. At this time, participants will have the study explained, questions answered, complete the necessary screening questionnaires (health history, PAR-Q+), complete an Accu-Check blood glucose test, and, if deemed eligible and interested, sign the informed consent. Upon enrollment, participants will also complete a food frequency questionnaire (DHQ-3), be assessed for body composition (BodPod), and have waist circumference measured. Participants will also be provided an ActiGraph accelerometer to objectively assess physical activity for the next seven days and scheduled for Visit 2 at least eight days later. Participants will be instructed not to purposely change dietary behaviors while enrolled in the study (i.e. start to diet).

Visits 2 and 3 (week 2 and 3). On the day of Visit 2, participants will record the specific foods, quantities, and time of day they consumed them prior to their testing visit. Participants will be instructed to eat the same foods at the same time of day prior to Visit 3 as they did prior to Visit 2. Visit 2 and 3 will be scheduled at the same time of day on the same day of the week where participants will be able to practice "usual" dietary behaviors, i.e. not on a holiday or a special occasion. Upon arriving to the LHBP exactly four hours post-prandial in the afternoon, participants will complete assessments for food reinforcement, attentional bias and inhibitory control for food cues before and twice after an acute bout of either exercise or sedentary activity, with one visit featuring exercise and the other visit featuring a sedentary activity. The order of the visits will be counterbalanced. Visual analog scales (VAS) will be performed for hunger and exercise enjoyment prior to each set of assessments. For female participants, these visits will occur while in the follicular phase, which will be assessed by a menstrual cycle questionnaire. Participants will wear the accelerometer to record physical activity during the washout period between assessment visits and be instructed to remain sedentary.

Acute Bout of Exercise. Participants will complete assessments of food reinforcement, attentional bias and inhibitory control before and after an acute bout of exercise during Visit 2 or visit 3 (depending on counterbalanced order). Participants will be provided a Polar A-300 heart rate monitor with smart-cal™ technology that factors the individual's sex, age, weight, activity level, and heart rate to produce an estimate of total energy in kilocalories (kcal) expended during the exercise session, with kcal expended displayed in real- time. Participants will engage in exercise on an elliptical ergometer (Octane Fitness ZR8) for the amount of time it takes them to expend 500 kcal

under supervision of a researcher in the laboratory. Participants will exercise at a self-selected intensity of at least 65% heart rate reserve (HRR), an intensity commonly prescribed for sedentary individuals beginning an exercise program. Based on previous studies conducted in our lab, 500 kcal of energy expenditure is attainable for even the most sedentary individual with exercise sessions lasting between 30 and 70 minutes depending on body mass and intensity of exercise. Prescribing the exercise bout on energy expenditure rather than duration or intensity will standardize the amount of total work being done across all participants. While both the intensity and duration of the exercise could be controlled, due to differences in body mass of the participants, either the exercise time or total work would still vary. An energy expenditure of 500 kcal is specifically used to ensure the exercise bout is of sufficient volume (intensity \* time) to produce weight loss if included in a long-term program and to elicit a dopaminergic response. Participants will be permitted to drink 0.5 l of water during and after the exercise bout. Participants will take a brief 15-minute rest after completing the exercise session before repeating assessments for food reinforcement, attentional bias and inhibitory control for food cues (post exercise assessment 1). Participants will repeat these assessments 60 minutes after cession of the exercise and sedentary activity bout (post exercise assessment 2).

**Acute Bout of Sedentary Activity.** Participants will complete assessments of food reinforcement, attentional bias and inhibitory control before and after an acute bout of sedentary activity (TV). Participants will watch TV for 60 minutes, choosing from a variety of television sitcoms (DVD) void of commercial advertisements that may feature food. Participants will have access to 0.5 l of drinking water during and after the test bout of TV viewing.

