Statistical analysis plan

Behavioral Mechanism of Energy Compensation with Exercise
NCT04651218

October 13, 2022

Statistical Analysis Linear mixed models will be fit with exercise and time as random effects to account for repeated measures and sex as a fixed effect. Response variables will be transformed if appropriate. With binary explanatory variables, an unstructured covariance matrix for the random effects will be assumed, but alternatives will be considered if needed. VAS scale ratings of hunger/satiety and exercise enjoyment will be assessed and included for adjustment as necessary. Power analysis: Because of our three response variables, we will use a Bonferroni corrected type I error rate of $0.05/3 = 0.017$ for our regression models. In a linear regression model with $n = 60$, 30 males and 30 females, counterbalanced to start with and without exercise and then crossing over to the other treatment, we will have 80% power to detect models with R squared of 20.4% or more (nQuery 8.5.1). Our mixed models will improve model fit and decrease variance estimates compared with linear regression, thus increasing power or decreasing R squared type measures that can be detected.

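### Activity before the two test visits is not matched: the sedentary instruction covers only the washout before Visit 3, and accelerometer wear is not stated to continue up to Visit 2

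*Protocol*

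**What the plan says.** The Protocol handles the two intervals differently.

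- **Visit 1 to Visit 2** (Visit 1, week 1). Participants are "provided an ActiGraph accelerometer to objectively assess physical activity for the next seven days and scheduled for Visit 2 at least eight days later". The only behavioural instruction concerns diet: "Participants will be instructed not to purposely change dietary behaviors while enrolled in the study (i.e. start to diet". Nothing is said about activity, and nothing says whether the device stays on after the seventh day.
- **Visit 2 to Visit 3** (Visits 2 and 3, week 2 and 3). "Participants will wear the accelerometer to record physical activity during the washout period between assessment visits and be instructed to remain sedentary".

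Other pre-visit conditions are aligned. On food the rule is "Participants will be instructed to eat the same foods at the same time of day prior to Visit 3 as they did prior to Visit" (the sentence ends by naming the first test visit). The two visits also share weekday and time of day, and testing starts four hours after eating. On sequence: "The order of the visits will be counterbalanced". Outcomes are assessed once before and twice after the bout at each visit.

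The SAP states: "Linear mixed models will be fit with exercise and time as random effects to account for repeated measures and sex as a fixed effect". It does not define time as visit order, names no period or sequence term, and gives no use for the accelerometer data.

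**The concern.** The comparison is one supervised exercise bout against one TV session in the same person. Recent exercise outside the laboratory is the behaviour most likely to blur that contrast. The Protocol restricts and records it before one test visit, but before the other it does not restrict it and may not record its last hours.

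Three things are at stake:

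- A participant allotted TV first could exercise shortly before Visit 2. That control session would not be free of recent exercise, and the planned record might not show it.
- Activity before Visit 2 can vary freely between people, while activity before Visit 3 is held down. This adds noise to the within-person difference.
- If the response to the bout depends on recent activity, exercise-first and exercise-second participants supply responses from different starting states, and the pooled estimate averages them.

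**Working it through.** **1. The two intervals side by side**

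| Before the test visit | Visit 2 | Visit 3 |
|---|---|---|
| Instruction to stay sedentary | none stated | yes, during the washout |
| Accelerometer | seven days after Visit 1; continuation to the visit not stated | worn during the washout |
| Food and its timing | recorded on the day | repeated from Visit 2 |
| Weekday and clock time | reference | same |

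The difference follows visit order, not condition. With n = 60 and equal orders (an assumption; the Protocol says only that order is counterbalanced), 30 exercise and 30 TV sessions fall at Visit 2 without the instruction, and 30 of each fall at Visit 3 with it.

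**2. How much time before Visit 2 may be unrecorded**

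Take Visit 1 as day 0 and Visit 2 at the minimum, day 8.

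- *Calendar days 1 to 7 worn:* the day before the visit (day 7) is recorded. Only the hours before the visit on day 8 are not.
- *Seven 24-hour periods from hand-out:* wear ends at 7 × 24 = 168 h. A visit at 8 × 24 = 192 h leaves 24 h unrecorded.
- *A later Visit 2:* each further day adds one day to either figure, unless the device is kept on.

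The gap is therefore at least some hours, and up to a day or more.

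**3. The plan's power figure, reproduced for reference**

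Inputs from the SAP: n = 60, alpha = 0.05/3, R squared = 0.204, power 80%. The number of predictors k is not given. For the overall F test, lambda = n × R²/(1 − R²) = 60 × 0.204/0.796 = 15.4, with k and n − k − 1 degrees of freedom. With k = 3 (3 and 56 df) power is 79.9%, and the R squared detectable at 80% power is 20.4%. The figure reproduces. The present point does not depend on it.

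**4. What an additive visit-order shift would do**

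The documents give no size for such a shift, so this is an illustration. Let p be the shift from Visit 2 to Visit 3, in SDs of the within-person exercise-minus-TV difference, and let T be the true effect. Exercise-first participants then have mean difference T − p, and exercise-second participants T + p.

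- Bias of the pooled mean = p × (n2 − n1)/60, where n1 is the number exercise-first and n2 the number exercise-second. At 30/30 this is 0 for any p. At an assumed 36/24 split its absolute value is 0.2p.
- SD of the pooled difference at 30/30, with no visit-order term and a single measurement per visit, = √(1 + p²).
- Two-sided critical value at 0.05/3 = 2.394. An effect with 80% power when p = 0 has standardised size 2.394 + 0.842 = 3.236. Power with the shift = Φ(3.236/√(1 + p²) − 2.394).

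| Assumed p | Bias, 30/30 | Absolute bias, 36/24 | SD factor, 30/30 | Power, 30/30 |
|---|---|---|---|---|
| 0 | 0 | 0 | 1.00 | 80% |
| 0.2 | 0 | 0.04 | 1.02 | 78% |
| 0.5 | 0 | 0.10 | 1.12 | 69% |
| 0.8 | 0 | 0.16 | 1.28 | 55% |

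These losses are an upper illustration. They ignore the pre-bout assessment, and a constant shift would cancel from within-visit change. A visit-order term would also recover them. Neither device removes person-to-person variation in how prior activity alters the response to the bout, nor a change in that response between starting states.

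**The case against.** The case against is substantial, and most of it stands as a limit on the point.

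- **Monitoring before Visit 2 exists.** A reader might infer that Visit 2 is unmonitored, or that everyone has at least a full unrecorded day before it. The text does not support either. Seven days are recorded, and on the calendar count the day before a day-8 visit is covered. Nor does the Protocol say that the device comes off on day seven.
- **The interval is not open-ended as planned.** No maximum is stated, but the section heading places Visit 2 in week 2.
- **Participants may already be inactive.** A reader might infer that nobody is screened for activity. The public text contains no eligibility section, so this cannot be concluded. The instruction to stay sedentary and the references to sedentary individuals under Acute Bout of Exercise suggest an inactive sample. If so, usual and instructed activity would differ little.
- **The design already protects the mean contrast.** Order is counterbalanced, and each visit has its own pre-bout assessment, so a shift in level is removed. The SAP does not state a change score or baseline adjustment, but the measurements are there to use.
- **The difference has a plausible reason.** Week 1 appears meant to record habitual activity; the later rule protects a washout. That explains seven days without restriction. It does not explain leaving the short period just before Visit 2 uninstructed.

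**Conclusion.** The point holds as a modest design weakness. Prior activity is restricted and recorded before Visit 3, while before Visit 2 it is unrestricted and possibly unrecorded for the last hours or longer. The Protocol matches the other main pre-visit conditions and gives no reason for treating activity differently.

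A reader might infer that the exercise effect is biased. The documents do not support that: the asymmetry follows visit order, and with balanced orders an additive shift contributes zero to the mean contrast. What remains is possible recent exercise before some Visit 2 TV sessions (at most the 30 TV-first participants if orders are equal), extra within-person variance, and any interaction between prior activity and the exercise response. Their size cannot be derived from the documents. The power losses in the table rest on assumed shifts and on an analysis that uses neither the pre-bout measure nor visit order. The change is worth making because it is cheap and because unrecorded hours cannot be recovered afterwards.

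**What to change.** 1. Keep the seven-day habitual-activity recording after Visit 1 as it is.
2. After it ends, apply the Protocol's existing activity instruction before Visit 2 as before Visit 3, over a short common window, for example the day before and the day of testing. Visit 2 would need to be booked so that this window falls after the seven recorded days.
3. State that the ActiGraph stays on until arrival at Visit 2.
4. Review both pre-visit records by one rule, with the definition of exercise on the device record fixed in advance; the documents give none. Flag visits preceded by exercise and add a sensitivity analysis to the SAP that excludes or adjusts for them.

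Flagging is preferable to mandatory rebooking. Both visits must share weekday and time of day and, for women, fall in the follicular phase, so a rebooked visit could miss that window.

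The cost is one added instruction, a day or so of extra wear of a device already issued, slightly more participant burden, and a short addition to the SAP.

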Statistical analysis plan

Behavioral Mechanism of Energy Compensation with Exercise
NCT04651218

October 13, 2022

Statistical Analysis Linear mixed models will be fit with exercise and time as random effects to account for repeated measures and sex as a fixed effect. Response variables will be transformed if appropriate. With binary explanatory variables, an unstructured covariance matrix for the random effects will be assumed, but alternatives will be considered if needed. VAS scale ratings of hunger/satiety and exercise enjoyment will be assessed and included for adjustment as necessary. Power analysis: Because of our three response variables, we will use a Bonferroni corrected type I error rate of $0.05/3 = 0.017$ for our regression models. In a linear regression model with $n = 60$, 30 males and 30 females, counterbalanced to start with and without exercise and then crossing over to the other treatment, we will have 80% power to detect models with R squared of 20.4% or more (nQuery 8.5.1). Our mixed models will improve model fit and decrease variance estimates compared with linear regression, thus increasing power or decreasing R squared type measures that can be detected.

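### As written, the SAP makes exercise a random effect, so its model has no mean exercise-versus-sedentary effect to test at 0.05/3, and no post-bout contrast is named

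*SAP*

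**What the plan says.** The model sentence in the SAP's Statistical Analysis paragraph gives each term a role: "Linear mixed models will be fit with exercise and time as random effects to account for repeated measures and sex as a fixed effect". On the random part it adds: "With binary explanatory variables, an unstructured covariance matrix for the random effects will be assumed, but alternatives will be considered if needed". The only other candidate terms are covariates: "VAS scale ratings of hunger/satiety and exercise enjoyment will be assessed and included for adjustment as necessary". Each of the three response variables is allotted 0.05/3, and the power statement for 60 participants reads: "we will have 80% power to detect models with R squared of 20.4% or more".

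The Protocol, under Visits 2 and 3, has each participant assessed "before and twice after an acute bout of either exercise or sedentary activity". Every participant receives both conditions in a crossover, "with one visit featuring exercise and the other visit featuring a sedentary activity". The section on the acute bout of exercise places the first post-bout assessment after a 15-minute rest and then says: "Participants will repeat these assessments 60 minutes after cession of the exercise and sedentary activity bout".

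Neither document mentions a fixed exercise term, a condition-by-time term, a primary time point or a contrast.

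**The concern.** A random effect suits a factor whose levels are a sample from a population and whose variance is of interest. Exercise versus sedentary activity is the comparison the trial exists to make, and the three assessments are a set schedule. If both sit only in the random part, their means are constrained to zero. The fit then returns a variance for exercise, and shrunken person-level predictions, but no estimate of how far or in which direction exercise moves food reinforcement, attentional bias or inhibitory control.

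A second gap remains if fixed means were intended. With one pre-bout and two post-bout values under each condition, the exercise effect could be an overall coefficient, a difference in change, or a post-bout difference adjusted for the pre-bout value. It could also be averaged over the two post-bout times or taken at one of them. The reference to binary explanatory variables does not say how three assessments are coded. The tested quantity is therefore left to be chosen after the data are seen.

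**Working it through.** **1. The plan's own figure.** Inputs from the SAP: n = 60, alpha 0.05/3 = 0.0167, power 80%, R squared 20.4%. The number of predictors k is not given. The overall F test has k and n - k - 1 degrees of freedom and noncentrality n·R²/(1 - R²) = 60 × 0.204/0.796 = 15.4.

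| k | 1 | 2 | 3 | 4 | 5 | 6 |
|---|---|---|---|---|---|---|
| Minimum R² at 80% power | 15.5% | 18.4% | 20.4% | 22.1% | 23.6% | 24.9% |

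Power at 20.4% is 92%, 86%, 80% and 74% for k = 1 to 4. Only k = 3 reproduces the SAP (20.43%, power 0.799). Exercise, time and sex would make three; so would exercise, binary time and their interaction. The figure gives a count of predictors and does not identify them. It also tests the whole model rather than exercise.

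**2. What the literal model estimates.** The SAP names neither a grouping factor nor a random intercept. Taking participant as the grouping factor, with a random intercept, the model is

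y = β0 + β1·sex + b0 + b1·exercise + b2·time + error, with each b having mean zero.

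If the true exercise effect has mean δ and between-person SD τ, the fit puts about τ² + δ² into the variance of b1. With τ = 0.5 (assumed):
- δ = 0: 0.25
- δ = +0.4: 0.25 + 0.16 = 0.41
- δ = -0.4: 0.25 + 0.16 = 0.41

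A simulation used 60 participants with six observations each, assumed intercept SD 1 and residual SD 0.7, exercise as the only random slope, and 60 runs per setting. It gave variances of 0.25, 0.41 and 0.41, and the only fixed terms were the intercept and sex. Adding a fixed exercise term recovered means of about 0.00, +0.39 and -0.41, with the variance back near 0.25 each time.

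**3. What the unnamed contrast is worth.** The documents give no SDs. Assumed: residual SD 0.6, and participant-by-visit SD v = 0, 0.3 or 0.6. The person effect cancels within participant. Standard errors for n = 60:
- Main effect over three assessments: √[(2v² + 2 × 0.36/3)/60]
- Post-minus-pre, post-bout values averaged: √[2 × (0.36/2 + 0.36)/60] = √(1.08/60)
- Post-bout difference between visits regressed on the pre-bout difference: √{[2v² + 0.36 - (2v²)²/(2v² + 0.72)]/60}

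| Contrast | SE at v = 0 / 0.3 / 0.6 | Estimate if effect is 0.5 at both post-bout times | Power at 0.05/3 (10,000 runs) |
|---|---|---|---|
| Main effect | 0.063 / 0.084 / 0.126 | (0 + 0.5 + 0.5)/3 = 0.33 | 99.7 / 93 / 57% |
| Post-minus-pre | 0.134 / 0.134 / 0.134 | 0.50 | 89 / 89 / 89% |
| Post-bout adjusted for pre-bout | 0.077 / 0.092 / 0.110 | 0.50 | 100 / 99.7 / 98% |

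If the effect is 0.5 and then 0.25, the main effect estimates 0.75/3 = 0.25 and the other two 0.75/2 = 0.375. With no effect, all three reject in 1.6% to 1.8% of runs, close to the nominal 1.67%.

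**The case against.** The strongest reply is that the sentence is shorthand for random slopes around fixed means. The SAP speaks of binary explanatory variables in the plural, and sex is the only binary term it calls fixed, so exercise or time must be among them. A regression on sex alone would give 15.5%, whereas 20.4% needs three predictors. A participant-level structure also has to be read in before the model can be fitted at all, and that is already halfway to the usual random-coefficient model. This is good evidence of intent, and I accept it as the likelier reading. It does not put a fixed exercise term into the text, and it does not say which contrast is tested.

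A reader might go further and infer that the trial runs a high false-positive risk: each person has one visit per condition, so a test of the exercise variance would pick up ordinary visit-to-visit variation. The documents do not support that. The SAP plans no test of a variance component, and any rejection rate worked out for one is hypothetical.

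A reader might also infer that an additive main-effect test would be invalid, or that adjustment for the pre-bout value is always the most precise choice. Neither holds. The main-effect test keeps its level, and under the assumed SDs it has the smallest standard error at v = 0 and 0.3. Its limitation is that it averages in the pre-bout value. Choosing among valid contrasts is partly preference; the fault is that no choice is recorded.

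**Conclusion.** The point stands as a defect in a stated rule, and it should be corrected before analysis. That the literal model lacks a mean exercise effect, an interval and a direction follows from the sentence itself and needs no assumed SD. The error is probably one of wording, so I do not predict that the trial will be analysed that way.

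The missing contrast matters on either reading. With equal effects at both post-bout times, a main effect over all three assessments understates the post-bout effect by one third. Under the assumed SDs, power for the three candidates ranges from 57% to 98% when visit-to-visit variation is large. These power figures are illustrations. The SAP's 20.4% is arithmetically sound with three predictors and is not in dispute.

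**What to change.** Replace the model sentence with one that states:
- fixed effects: condition (exercise or sedentary), time (three levels), condition-by-time and sex;
- participant-level random terms: an intercept, plus a condition slope or a participant-by-visit effect;
- one named contrast per outcome, tested at 0.05/3.

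In this model the pre-bout value is a response, so the natural contrast is the exercise-minus-sedentary difference in post-minus-pre change. It can be averaged over the two post-bout assessments or taken at one named as primary.

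An alternative is a separate model with only the post-bout values as responses and the same-visit pre-bout value as a covariate. Under the assumed SDs this is more precise than post-minus-pre; the standard errors above are for the within-participant version. The pre-bout value should not be both response and covariate. If a main effect over all three assessments is preferred, the SAP should say that it includes the pre-bout value and is not the post-bout effect.

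The cost is a few sentences, with no new data or participants. The detectable R squared must be restated: 22.1% with four predictors (condition, binary time, their interaction, sex), or 24.9% with six (1 condition + 2 time + 2 interaction + 1 sex). Better, it can be replaced by power for the named contrast: a two-sided paired test with n = 60 at 0.05/3 has 80% power for a standardized within-person difference of about 0.43.

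### The SAP names no fixed exercise effect and no post-bout contrast; the likeliest reading of its model returns two thirds of a sustained exercise effect

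*SAP*

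**What the plan says.** The Protocol (Visits 2 and 3) has participants complete tests of food reinforcement, attentional bias and "inhibitory control for food cues before and twice after an acute bout of either exercise or sedentary activity". The section on the acute bout of exercise places the first post-bout set after a 15-minute rest and the second 60 minutes after the bout ends. Each person therefore gives three scores per outcome at each of two visits. On visit order, the Protocol says: "The order of the visits will be counterbalanced".

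The SAP (Statistical Analysis) describes the model as linear mixed models with "exercise and time as random effects to account for repeated measures and sex as a fixed effect". It adds: "With binary explanatory variables, an unstructured covariance matrix for the random effects will be assumed". The only adjustment variables it names are the VAS ratings, to be used if needed. It does not mention an exercise-by-time term, the coding of time, visit order, a contrast at or across the post-bout times, or any role for the pre-bout outcome score. The Protocol contains no analysis text that supplies these.

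Power is stated for a linear regression with n = 60 and a type I error rate of 0.05/3 = 0.017: "we will have 80% power to detect models with R squared of 20.4% or more". The number of predictors is not given. The SAP then says "Our mixed models will improve model fit and decrease variance estimates compared with linear regression", without a figure.

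**The concern.** Neither document states an estimand. A crossover with scores before and twice after each bout points to the exercise-minus-sedentary difference after the bout. The stated model does not isolate that difference.

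- **Literal reading.** The fixed part is an intercept and sex. The random exercise effect describes how much people differ in their response. No parameter holds the mean response, so there is nothing to test.
- **Additive reading.** Exercise, time and sex are also fixed main effects. The exercise coefficient then averages the condition difference over all three assessments, including the one made before any exercise.

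At stake are the size of the reported effect, the power of the test, and the freedom to choose a contrast after the data are seen. The Bonferroni division by three covers three outcomes. It does not cover several possible contrasts within each.

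**Working it through.** **1. The plan's own figure.** Inputs from the SAP: n = 60, alpha = 0.017, R² = 0.204. The overall F test with k predictors has k and n − k − 1 df and noncentrality n·R²/(1 − R²) = 60 × 0.204/0.796 = 15.38. As k is not stated, several values were tried:

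| k | Power at R² = 20.4% |
|---|---|
| 1 | 92.5% |
| 2 | 86.0% |
| 3 | 80.1% |
| 4 | 74.7% |

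The figure reproduces with k = 3. That fits exercise, time and sex as single-df terms, but other sets of three predictors are possible. It makes the additive reading more likely than the literal one; a regression on sex alone (k = 1) does not reproduce it. It does not show whether an interaction was intended.

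**2. What the additive coefficient estimates.** Take balanced data, no mean pre-bout difference, and post-bout differences d₁ and d₂. The coefficient is (0 + d₁ + d₂)/3.

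- Effect d at both post-bout times: 2d/3 = 0.667d.
- Effect d at one post-bout time only, whichever it is: d/3 = 0.333d.

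Noise-free least squares gives the same values whether time has three levels or is coded pre/post.

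**3. Cost in precision for a sustained effect d.** The documents give no SDs, so these are assumptions: v = visit SD (shared by the three scores of a visit), s = residual SD, h = SD between people of the post-bout response to exercise. Variances of the exercise-minus-sedentary difference per person, scaled to estimate d:

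- Additive: 2(v² + s²/3)/(4/9) + h²
- Baseline-adjusted post-bout average: 2(v² + s²/2 − v⁴/(v² + s²)) + h²

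With s = 1, the ratio of variances is the ratio of participants needed:

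| v/s | h = 0 | h = s |
|---|---|---|
| 0 | 1.50/1.00 = 1.50 | 2.50/2.00 = 1.25 |
| 0.5 | 2.625/1.40 = 1.88 | 3.625/2.40 = 1.51 |
| 1 | 6.00/2.00 = 3.00 | 7.00/3.00 = 2.33 |

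The h = s column matters because the SAP itself makes exercise a random effect.

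**4. How the pre-bout score enters.** Suppose an interaction is added but the pre-bout means are left free in each condition. The natural contrast is then the difference in change from baseline. Its variance at h = 0 is 2(s² + s²/2) = 3s², against 1.00, 1.40 and 2.00 for the adjusted average. The ratios are 3.00, 2.14 and 1.50, so at v/s of 0 and 0.5 this is less efficient than the additive model. The pre-bout score should therefore be a covariate, or its mean should be held equal across conditions.

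**5. Power for the contrast of interest.** For one within-person contrast with n = 60, alpha = 0.05/3 and 80% power, use a noncentral F with 1 and 58 df and noncentrality 60·δ². This gives δ = 0.43 SD of the (adjusted) within-person difference.

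**The case against.** The best defence is that the SAP uses ordinary random-slope language. The random effects are there to handle repeated measures, and an analyst would supply matching fixed effects without being told. The three-predictor reproduction supports this, and that part stands. A reader might infer that the trial will report no mean exercise effect; the wording permits that, but the documents do not show that it was intended. The defence still leaves the additive model, whose coefficient is diluted.

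A reader might also infer that two analysts could report effects differing by a factor of 1.5. That needs a second reading in which time means only the two post-bout assessments and the pre-bout data are dropped. Nothing in either document suggests dropping them.

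It is fair, too, that the participant ratios depend on assumed SDs and shrink when people differ in their response. The direction survives and the size does not, which is why both columns are shown.

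Finally, the pre-bout score is not needed to remove bias, because visit order is counterbalanced. Its role is precision, and if visit-level variation is zero, adjustment gains nothing. Post-only analysis without the baseline costs little at moderate visit variation: at v/s = 0.5 and h = 0, 2(0.25 + 0.5)/1.40 = 1.07 times the participants. So the case for naming the baseline's role is that it should be fixed in advance, not that leaving it out would mislead.

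**Conclusion.** The point holds as a gap in specification that should be fixed. Followed literally, the model gives no mean exercise effect. On the likelier additive reading it gives 2/3 of a sustained effect, or 1/3 of an effect at one post-bout time, assuming balanced data and no mean pre-bout difference. The loss of precision for a sustained effect ranges from 1.25 to 3.00 times the participants over the assumed SDs shown, and no single value can be claimed.

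Three stronger conclusions are not supported. The documents do not show a biased comparison of conditions: the additive coefficient correctly estimates an average over three times, but that is the wrong average for a post-bout question. The 20.4% is not an arithmetic error, since it reproduces. Its fault is that it refers to the whole model, which sex or time alone could satisfy, so it is not power for an exercise effect. And the three-predictor match does not prove which terms were planned.

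**What to change.** In the SAP:

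- State exercise, time (pre, post 1, post 2), exercise-by-time, sex and visit order as fixed effects.
- Use participant random effects that include a random exercise effect, or an unstructured within-person covariance.
- Say how the pre-bout score enters: as the reference level of time with its mean constrained equal across conditions, or as a covariate.
- Pre-specify one primary contrast per outcome at 0.05/3, by default the average post-bout exercise-minus-sedentary difference. Report both time-specific estimates with intervals.
- Replace the R² statement with power for that contrast: about 0.43 SD of the within-person difference at n = 60 and 80% power.

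The cost is SAP wording and a redone power statement, as every measurement is already planned. The main trade-off is that an average contrast loses power if the effect fades by 60 minutes: an effect d at one time only contributes d/2. If fading is thought plausible, a joint 2-df test of exercise at post 1 and post 2 could be made primary instead. Its detectable effect is 0.47 SD rather than 0.43 when the effect is equal at both times, about 23% more participants.
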